Severe Perinatal Depression (PND) is a major depressive episode that occurs during pregnancy or onset within 12 months of the birth of a child. The prevalence of severe PND in the general population is estimated to be 5-10% (2). PND is a seriously disabling condition and can increase the risk of self-harm and health complications in mother can deleteriously affect the cognitive, emotional and social development of the child and increases the substantial economic burden on families and society (3). Selective Serotonin Reuptake Inhibitors (SSRIs) and psychotherapy are the main available treatment modalities for PND. While they are effective in some, it takes longer to work and half of the patients do not fully recover from depression. A faster onset of antidepressant action will be critical in enabling faster relief from depression and may increase the chance of full recovery. The main objective of this study is to investigate the rapid antidepressant effect of low sub-anesthetic dose of ketamine in PND.

Aims

To assess the safety, pharmacokinetics and antidepressant efficacy of a sub-anesthetic dose of intravenous ketamine in perinatal depression

A single, intravenous, sub-anesthetic dose of ketamine in patients with Treatment-Resistant Depression (TRD) induces a significant (50%) reduction in depression symptoms within 2 hours of administration with 65% of depressed patients respond by 24 hours and up to 35% maintain response until the end of 1 week (4). Our in-house pilot data, in consistent with worldwide studies, show that ketamine (N=5) can be safely administered to depressed patients and improves depression symptoms when assessed at 24 hrs post infusion. Ketamine has not been studied in the treatment of PND where there is a significant unmet need.

The dosing of ketamine (0.5 mg/kg over 40 mins) for antidepressant treatment was developed from research studies in the 1990s based on use in healthy participants (36). However, newer studies show some patients respond to lower dose and tolerated better (fewer side effects) by the patients (37). IV Ketamine reaches a peak within a few mins with an elimination half-life of 2–3 hrs (38). Ketamine's clearance may be 20% higher in women than in men (39). Ketamine is mostly metabolized in norketamine (80%) and persists more than 5 h after administration (38). It is important to evaluate ketamine's pharmacokinetic data in PND to improve safety for the

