breastfeeding mother and the baby. Ketamine and its metabolites will be evaluated in PND patients receiving ketamine 0.5 mg/kg or 0.2 mg/kg at 30 mins, 2 hours and 4-5 hrs after ketamine infusion. All adverse medical and psychiatric events with onset or worsening after the administration of ketamine will be included in the analysis.

The proposed experiment will be a proof-of-concept study in which we will evaluate the safety, pharmacokinetics, and efficacy of ketamine 0.5 mg/kg and 0.2 mg/kg over 40 minutes in a double-blinded and crossover fashion separated over one week (5) (dose used in antidepressant clinical trials) in PND patients who are not currently breastfeeding. The primary outcome measure of efficacy will be the Hamilton Depression Rating Scale (HAM-D-17) at 24 hours and additional secondary anxiety and mood scales. (6). Any adverse medical and psychiatric events will be recorded and summarized. Ketamine and its metabolites will be evaluated at 30 mins, 2 hours and 24 hrs.

Hypothesis 1): Ketamine will significantly decrease (>50%) in HAM-D17 scores at 24 hrs after infusion from baseline. The 0.5 mg/kg dose will be more efficacious than 0.2 mg/kg in improving depression symptoms.

Hypothesis 2) Ketamine will improve anxiety symptoms in PND (as measured using HAM-Anxiety and EPDS) at 24 hrs after infusion in patients with PND. Anxious subtypes are the most common subtype during a late postpartum period representing about 70 % of PND. (40)

Hypothesis 3) Ketamine infusion will be tolerated well by the patients with fewer side effects at 0.2 mg/kg compared to 0.5 mg/kg.

METHODS

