Before the infusion, the psychiatrist and anesthesiologist will evaluate the patient. During the infusion, patients will be asked constantly about "how they feel" and will be monitored continuously by the registered nurse under the supervision of an Anesthesiologist. EKG and pulse-oximetry will be monitored throughout the procedure to

check for hemodynamic changes. After the completion of 40 min infusion, patients will rest for two-four hours under the observation of clinical nurse.. After the infusion both psychiatrist and anesthesiologist will evaluate the patient. Patients may complete clinical questionnaires after this session at HCPC or CRU for approximately 30 minutes. After the first infusion, patients will be contacted one day after over the phone and after the second infusion, patients will be contacted one day after and 7 days after the infusion. During the phone call, patients will be asked about their physical health, will be asked about adverse events and respond questionnaires that evaluate mood status.

Recruitment: The current project will ensure robust and timely recruitment through coordination with ongoing studies at the UT Center of Excellence on Mood Disorder (CEMD) ([name], Departmental Chair). [name] runs a perinatal clinic focused on pregnant or postpartum women with mood disorders in the psychiatry department. [name] also collaborates with [name], UTHealth Department of Obstetrics, Gynecology and Reproductive Sciences on a postpartum research project. Additionally, a large research participant registry has been set up by this UT center (n = 4952 over the last 5 years, of which 80% have a mood disorder history).

Recruitment will also be facilitated through the UT Research Match program. On average, 200 patients have a higher report of depression and mental health problems in the last year and of which nearly 100 patients had higher EPDS scores that meet PND criteria. The perinatal psychiatry clinic will facilitate clinical recruitment. Subject recruitment will include initial identification of cohort pool using selection criteria and subsequent review of identified patient records before final vetting and consent.

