IRB NUMBER: HSC-MS-18-0416
IRB APPROVAL DATE: 06/26/2019

Urine pregnancy test	X	X		X			
Vital Signs	X	X		X			
Height and Weight measurement	X						
Blood Collection		X	X ¹	X	X ²		
Structured Clinical Interview for DSM-IV Axis I Disorders (SCID-I)	X						
Hamilton Depression Rating Scale (HAM-D-17)	X	X	X	X	X	X	X
Montgomery-Asberg Depression Rating Scale (MADRS)	X	X	X	X	X	X	X
Edinburgh Postnatal Depression Scale (EPDS) scale	X	X	X	X	X	X	X
Young Mania Rating Scale (YMRS)	X		X		X		
Clinical global improvement (CGI)	X		X		X		
Brief Psychiatric Rating Scale (BPRS)	X		X		X		
Generalized Anxiety Disorder (GAD-7)	X	X	X	X	X	X	X
Columbia Suicide Severity Rating Scale (C-SSRS)	X		X		X		
Hamilton Anxiety Rating Scale (HAM-A)	X		X		X		
Snaith-Hamilton pleasure scale (SHAPS)	X		X		X		
Beck Depression Inventory (BDI)	X	X	X	X	X	X	X
AE Report	X		X		X	X	X
Concomitant Medications	X		X		X		
Study Contact Card given			X		X		

¹ Done at 30 minutes after infusion (+/-10), 2 hours after infusion (+/- 30 minutes) and 4.5 hours after infusion. IRB NUMBER: HSC-MS-18-0416

Patients that are unable to arrive to the appointment with a caregiver will be reimbursed for 1-2 hours of transportation to and from the infusion days. They will receive a phone call that same day to ensure safe arrival home. UTH Health IRB APPROVAL DATE: 06/26/2019

All of the above clinical questionnaires will be completed at the screening visit as well as on the ketamine infusion day, except the SCID-I, which will only be completed at the screening.

All data collected on paper forms will be stored in locked cabinets, while electronic data is stored on our secure password protected server (maintained by the UTHealth Medical School Information Technology Department). All electronic records will identify study participants only by a study code, and the electronic file linking codes to individual identifiers will be destroyed once data collection is complete.

Patients will arrive fasting from midnight on study visit day have blood draws and complete questionnaires at our clinical research suite at UTHealth's Biomedical and Behavioral Sciences building (BBSB) at [name] or at UTHealth CRU at Memorial Hermann-TMC, Houston. University of Texas Health Science Center at Houston Memorial Hermann-TMC [name] or at UT Health Harris County Psychiatric Center (HCPC)

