Ketamine infusion: The most commonly reported side effects during the 4 hour period after each infusion include feeling strange or unreal (58.3%), abnormal sensations (54.2%), blurred vision (50.0%), feeling sleepy or sleepy (48.5%) and headaches (30-40%). Based on previous evidence, we do not expect ketamine to impair

cognitive functions such as memory, attention or language. If patients are currently taking certain medications on a daily basis within 24 hours prior to and/or after receiving ketamine, they will not be able to take these medication(s) while receiving a ketamine infusion without clearance or approval of the physicians involved in administering ketamine. Medications include: Sedatives (e.g., clonazepam, lorazepam, alprazolam); Antibiotics (e.g., azithromycin, clarithromycin); Antifungal agents (e.g., ketoconazole); Tramadol. This is due to concerns for potentially increased sedation or trouble breathing. One third of the patients exposed to standard repeated infusions of IV ketamine reported some kind of hemodynamic change such as elevated blood pressure (BP) and/or heart rate (Murrough et al., 2013b) that usually resolves shortly after the ketamine infusion (aan het Rot et al., 2010; Murrough et al., 2013b). It has been reported that initial hypertensive episodes and transient tachycardia are predictive of hemodynamic changes with subsequently repeated ketamine infusions (aan het Rot et al., 2010). Ventricular premature contractions, hypotension, and non-significant changes in oxygen saturation have also been reported with low-dose (0.5mg/kg) ketamine infusions over 40 minutes.

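### Hypothesis 3 compares side effects between doses, but no structured measure of acute perceptual effects is scheduled near the end of infusion, and BPRS and YMRS lack a same-day baseline and a fixed rating time

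*Combined protocol and SAP*

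**What the plan says.** The protocol compares "ketamine 0.5 mg/kg and 0.2 mg/kg over 40 minutes in a double-blinded and crossover fashion separated over one week". Hypothesis 3 (Primary Hypotheses and Specific Aims) reads "Ketamine infusion will be tolerated well by the patients with fewer side effects at 0.2 mg/kg compared to 0.5 mg/kg". The Justification section gives the same aim, comparable efficacy with fewer side effects at a lower dose, as the reason for having no placebo group.

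The expected effects are listed under Potential Risks/Discomforts: feelings of unreality (58.3%), abnormal sensations (54.2%) and blurred vision (50.0%), over the four hours after each infusion. The Confidentiality paragraph of that section describes side effects as transient.

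On measurement:

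- **Schedule of assessments.** BPRS and YMRS are marked at screening and in the After Infusion column on both infusion days, with nothing under Before Infusion. HAM-D, MADRS, EPDS, GAD-7 and BDI are marked both before and after. The text below the table puts all questionnaires except the SCID-I on the infusion day, without saying before or after.
- **Research Design and Methods.** After the 40-minute infusion, "patients will rest for two-four hours under the observation of clinical nurse". The psychiatrist and anesthesiologist then evaluate the patient, and next comes "Patients may complete clinical questionnaires after this session at HCPC or CRU for approximately 30 minutes". During the infusion patients are asked how they feel; no scale is named.
- **Medical Monitoring.** The rest is two hours, with reassessment at two hours.
- **Data Analysis Plan.** The safety and tolerability measures are treatment-emergent AEs and changes in EPDS, GAD-7, PHQ-9 and C-SSRS. BPRS and YMRS are not named.

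**The concern.** The side effects that should separate the two doses are expected during the infusion and soon after it. The named tolerability scales cover mood, anxiety and suicidality. BPRS is in the trial and could record perceptual and thought disturbance, but it is not scheduled near the peak, has no reading from the same morning, and has no set time afterwards. Because the rating time is open and worded as optional, it could also differ between a patient's two visits, which would add noise to the comparison the crossover is meant to sharpen.

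At stake is how well the trial can answer Hypothesis 3. With 10 patients, that comparison would rest on AE reports for which no fixed method of enquiry is described.

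**Working it through.** **The plan's own figures.** The documents give no figure for rating time or exposure. Their one power statement concerns efficacy (N = 10, d = 1.2, one-sided 0.05, 95% power). A paired t-test with noncentrality 1.2 × √10 gives 0.967, so the statement reproduces; it does not bear on this point.

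**Inputs for exposure.** Doses are 0.5 and 0.2 mg/kg over 40 minutes. The Aims say "IV Ketamine reaches a peak within a few mins" "with an elimination half-life of 2–3 hrs". The rest is 2 h or 2–4 h. I assume one-compartment decline, a peak at the end of infusion, and levels proportional to dose.

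**Formula.** Fraction remaining = 2^(−t / half-life), with t in hours from the end of infusion. Levels are in units where the end-of-infusion level equals the dose, so the starting gap is 0.5 − 0.2 = 0.3 and the starting ratio is 0.5 / 0.2 = 2.5.

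| t (h) | Half-life (h) | Fraction | 0.5 mg/kg level | 0.2 mg/kg level | Gap | Gap as % of start | Ratio |
|---|---|---|---|---|---|---|---|
| 0 | any | 1.000 | 0.500 | 0.200 | 0.300 | 100 | 2.5 |
| 0.5 | 2 | 0.841 | 0.420 | 0.168 | 0.252 | 84 | 2.5 |
| 0.5 | 3 | 0.891 | 0.445 | 0.178 | 0.267 | 89 | 2.5 |
| 2 | 2 | 0.500 | 0.250 | 0.100 | 0.150 | 50 | 2.5 |
| 2 | 3 | 0.630 | 0.315 | 0.126 | 0.189 | 63 | 2.5 |
| 4 | 2 | 0.250 | 0.125 | 0.050 | 0.075 | 25 | 2.5 |
| 4 | 3 | 0.397 | 0.198 | 0.079 | 0.119 | 40 | 2.5 |

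The absolute gap is 84–89% of its starting size half an hour after the infusion, 50–63% at 2 h and 25–40% at 4 h. The ratio does not change. The model omits the distribution phase, which would make the early fall faster, and norketamine, which the Aims say persists beyond 5 h and which could prolong active exposure.

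**The missing same-day baseline.** Write S for the single screening score. The within-patient dose contrast in change from screening is

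(post 0.5 − S) − (post 0.2 − S) = post 0.5 − post 0.2.

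S cancels, so illness change between screening and the first infusion does not bias the contrast. Change between the two infusions is a period effect, which the randomised and balanced order addresses. What the shared screening score cannot provide is

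(post 0.5 − pre 0.5) − (post 0.2 − pre 0.2),

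which adjusts for the patient's state on each day and shows whether she entered the second infusion where she entered the first. The second use matters here: the Aims cite response lasting to one week in up to 35% of patients, and the minimum interval is 7 days. The gain in precision depends on how closely same-day scores correlate, which the documents do not give.

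**The case against.** The strongest reply is that the plan does not use BPRS or YMRS to test Hypothesis 3. The protocol lists both among ratings of clinical symptoms, never calls them side-effect scales, and leaves them out of the analysis plan. AEs are recorded after each infusion and at follow-up, all adverse events that start or worsen after ketamine enter the analysis, and patients are monitored and questioned throughout the infusion. This stands. A reader might infer that the trial is set to declare the doses equally tolerated on the strength of late BPRS scores; no such analysis is planned.

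Four other inferences go too far:

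- **That the scales have no baseline.** Both have a screening value. Only the same-day value is missing.
- **That these are the only structured psychiatric safety scales.** C-SSRS is structured, has the same schedule, and is a named safety measure. It does not cover perceptual effects.
- **That the late 0.5 mg/kg level matches the 0.2 mg/kg peak, so the doses look alike.** On the model above, the 0.5 mg/kg level at 2 h is still 1.25–1.57 times that peak, and it reaches it only at 2.64–3.97 h. It is also the wrong comparison, because both doses are rated at the same time after infusion and their ratio remains 2.5.
- **That the scales are known to be rated after two to four hours.** This is inferred from the order of sentences. The schedule says only that the rating follows the infusion, and the physicians' evaluation might include BPRS.

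The published rates cover a four-hour window, so they do not show that the effects have gone by the time of a late rating. None of this supplies a structured rating near the peak, a fixed rating time, or a fixed AE checklist.

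**Conclusion.** The point holds as a gap in measurement for Hypothesis 3. No structured measure of perceptual or psychotomimetic effects is scheduled near the end of infusion, BPRS and YMRS have no same-day pre-infusion rating, and their post-infusion time is unspecified, with two descriptions of the rest period that must be reconciled.

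A rating 2–4 h after infusion would face 25–63% of the initial absolute concentration gap. That range assumes one-compartment decline with the protocol's half-life and dose-proportional levels. Reading it as a smaller difference in scores further assumes that acute effects follow plasma level. The documents give no concentration-effect relation, so the understatement cannot be sized. The missing same-day baseline costs precision and any check for carry-over; it does not bias the dose contrast through illness change before the first infusion.

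This does not undermine the efficacy comparison or its sample size. It is an inexpensive improvement that the sponsor should make, since tolerability by dose is a stated reason for the design.

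**What to change.** 1. Add BPRS, at least the perceptual and thought-disturbance items, immediately before each infusion and at one fixed time near its end: either the end of infusion or the 30-minute blood draw. Use the same time for both doses, and state whether it is counted from the start or the end of the infusion. Keep the later rating as a recovery reading.
2. Give a clock time for every post-infusion scale, and reconcile the rest period in Research Design and Methods with that in Medical Monitoring.
3. Elicit AEs with one fixed checklist of the side effects the protocol lists, at the same times for both doses.
4. In the Data Analysis Plan, name the within-patient 0.5 versus 0.2 mg/kg difference in pre-to-peak BPRS change as a supportive structured measure for Hypothesis 3, alongside AEs.

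The cost is a schedule edit and a few minutes of extra rating per infusion, with a scale, staff and visits already in the trial. The downside is that patients may be less cooperative near the end of infusion; the 30-minute draw is the alternative, at which 84–89% of the gap remains on the model above if the time is counted from the end of infusion.

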The Edinburgh Postnatal Depression Scale (EPDS) is the most commonly used screening tool for PND (2). Analysis of a large sample of EPDS (N=663) by international postpartum depression consortium (19 international sites) found that anxiety and anhedonia were the prominent symptom dimensions with post-partum onset in PND (8). **Moderate and severe anxious subtypes are the most common subtype during a late postpartum period representing about 70 % of PND.** Psychotherapeutic and pharmacological interventions are the current standard of care for moderate and severe PND. A systematic review of SSRIs have shown to have a modest effect in PND (Remission rates (46.0% vs. 25.7%; pooled risk ratio, 1.79)(9). However, current modalities take longer (>6 weeks for SSRI and >8-12 sessions for therapy)(3) but access to specialist therapists is not widely available (3). Despite some progress, nearly 50% of depressed patients do not unfortunately, fully respond to pharmacological treatment (10). The aetiopathogenesis of PND is less known and various neurobiological and psychosocial models have been proposed. Pregnancy is associated with marked changes in reproductive hormones (estradiol and progesterone) and therefore, such changes cause depression in vulnerable women (11). It is proposed that rapid changes in gonadal hormone may cause changes in brain γ -aminobutyric acid (GABA) and glutamate and therefore cause a **cortical excitatory-inhibitory imbalance**, which may contribute to depression (12). Interestingly novel neurosteroid **pregnenolone** is a positive allosteric modulator of γ -aminobutyric acid (GABA_A) receptors, has been showing promising treatment for post-partum

depression (12). Identifying novel therapeutic targets for PND is a critical priority as prolonged illness can lead to the poor functional outcome (3). Consequently, there are two primary challenges in antidepressant research: (a) developing rapidly acting, safe and effective antidepressant treatments, and (b) developing noninvasive clinically useful biomarkers of antidepressant response with a focus on early indicators of treatment response.

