Research Design and Methods: All human subjects' research will be conducted with full approval from the IRB at the University of Texas Health Science at Houston. We will recruit PND patients (N=10) who will be administered a single intravenous infusion of Ketamine either at 0.5 mg/kg or 0.2 mg/kg over 40 minutes in a double-blinded and crossover fashion separated by minimum 7 days, with the order being randomized and balanced across subjects. Two doses will help decide the safe, tolerable and effective dose for PND subjects will undergo a standard screening interview visit to confirm eligibility evaluations including SCID-4 interview (27) and collection of demographic, clinical and medical history. To ensure medical stability, each patient will have a physical examination and urine toxicology screen to rule out the recent undisclosed use of illicit substances. It will also be requested that the patient provide a record of lab results to indicate adequate health for inclusion.

We will pre-screen potential participants over the phone to minimize the invitation to non-eligible participants. Eligible patients that want to participate in the study will be scheduled to have a screening visit to review consent and determine eligibility.

The total duration of the commitment of the study is minimum of 4 weeks. Extension of the timeline can occur depending on the time between the screening visit and the first infusion dose. The total commitment should not exceed 3 months. There will be a minimum 7 days between the 2 infusions. Patients who qualify will complete the infusions on another day at UTHealth Clinical Research Unit at Memorial Hermann-TMC, Houston. University of Texas Health Science Center at Houston Memorial Hermann-TMC [name] or at our Harris County Psychiatric Center (HCPC) where they will be given the ketamine infusion by the study nurse. Patients will be advised to follow the American Association Preoperative Fasting Guidelines prior to infusion.

There will be two appointments where they will be administered a single intravenous infusion of Ketamine either at 0.5 mg/kg or 0.2 mg/kg over 40 minutes in the first infusion visit and a second infusion visit where they will receive the infusion that was not given on the first visit, where there will be a minimum of 7 days between infusions.

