Screening evaluation will obtain family history and demographic data. An estimated duration of a complete screening visit will be approximately 3 hours or less. Copies of any recent medical evaluations (past medical history, physical exam, etc.) will be requested from treating clinicians and health care providers. We will perform a urine drug screening (UDS) to rule out the recent undisclosed use of illicit substances. Also we will perform a urine pregnancy test. We will also complete a physical examination, height and weight and vital signs. Demographic information is obtained through a standardized form and covers: age, race, gender, education (information both on siblings and their parents), religion, and socioeconomic status.

Patients will complete mood questionnaires rating the severity of the clinical symptoms:

- 1) SCID-I Interview
- 2) Hamilton Depression Rating Scale (HAMD-17)
- 3) Montgomery-Asberg Depression Rating Scale (MADRS)
- 4) Edinburgh Postnatal Depression Scale (EPDS) scale
- 5) Young Mania Rating Scale (YMRS)
- 6) Clinical global improvement (CGI)
- 7) Brief Psychiatric Rating Scale (BPRS)
- 8) Generalized Anxiety Disorder (GAD-7)
- 9) Columbia Suicide Severity Rating Scale (C-SSRS)
- 10) Hamilton Anxiety Rating Scale (HAM-A)
- 11) Beck Depression Inventory (BDI)
- 12) Snaith-Hamilton pleasure scale (SHAPS) (29).

We will also collect exploratory data on subjective anhedonia (SHAPS) measurements to investigate ketamine's effect on specific reward and motivation functioning in this spectrum of psychiatric patients.

All aforementioned assessments may be administered in a standard manner involving researcher or self-report questionnaires on paper, or they may be administered using Qualtrics, which is a HIPAA compliant electronic data collection tool widely used in research. When the latter is used, participants will be invited to complete questionnaires on a computer or tablet.

Assessment	Screening (at BBSB)	Infusion Day 1 (at HCPC or CRU)		Infusion Day 2 (at HCPC or CRU)		Follow up post infusion 1 and again post infusion 2 Day 1 (by phone)		Follow up post infusion 2 Day 7 (by phone)
		Before Infusion	After Infusion	Before Infusion	After Infusion	Post infusion 1	Post infusion 2	Post infusion 2
Informed Consent	X							
Eligibility Review	X	X		X				
Demographics and Psychiatric/Medical History	X							
Physical Examination	X	X		X				
Assessment by anesthesiologist and psychiatrist.			X		X			
Urine Drug screen	X	X		X				

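### The anhedonia scale (SHAPS) is scheduled neither before an infusion nor at 24 hours, so its exploratory question can be addressed only weakly

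*Combined protocol and SAP*

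**What the plan says.** The section on clinical and diagnostic assessments lists SHAPS among the questionnaires and then states a purpose for it. The sentence opens with "We will also collect exploratory data on subjective anhedonia (SHAPS) measurements to investigate", and the object it gives is how ketamine acts on reward and motivation. It names no time point, dose contrast or analysis. The Data Analysis Plan does not mention SHAPS.

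The Background reports from a large consortium data set that "anxiety and anhedonia were the prominent symptom dimensions with post-partum onset in PND".

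In the schedule of assessments, the SHAPS row is marked at Screening, After Infusion on Infusion Day 1 and After Infusion on Infusion Day 2. Both Before Infusion cells and all telephone follow-up cells are blank. The rows for HAM-D-17, MADRS, EPDS, GAD-7 and BDI are marked before and after both infusions and at follow-up.

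Below the table, the text says: "All of the above clinical questionnaires will be completed at the screening visit as well as on the ketamine infusion day", with the SCID-I as the only exception. It does not say whether this means before or after dosing.

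The efficacy time point for HAM-D-17 is 24 hours (Primary Hypotheses and Specific Aims).

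**The concern.** An effect of an infusion is best read against a score taken just before that infusion, at a time when the acute drug state has passed. SHAPS has neither the reference nor the later reading.

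Three things follow. Change in SHAPS must be measured from screening, so it includes whatever happened between screening and the infusion. The only post-dose scores are taken on the infusion day, when sedation and altered sensation may colour the answers. With no score before infusion 2, nobody can see whether some effect of infusion 1 was still present.

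At stake is one exploratory result. SHAPS could not be set beside the 24-hour HAM-D-17 result, and in a trial of 10 patients a reading that was never scheduled cannot be recovered later.

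**Working it through.** **1. The plan's own figure.** No sample size or precision is stated for SHAPS. The stated N = 10 concerns HAM-D (effect size 1.2, 95% power, one-sided 0.05). An exact paired t calculation gives power 0.948 at n = 9 and 0.967 at n = 10, so 10 reproduces. The SHAPS point does not depend on it.

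**2. Schedule, row against row.**

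| Scale | Screening | Before infusions 1 and 2 | After infusions 1 and 2 | Telephone follow-up |
|---|---|---|---|---|
| HAM-D-17 | yes | yes | yes | yes |
| SHAPS | yes | no | yes | no |
| HAM-A | yes | no | yes | no |

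One follow-up cell was lost when the table was read from PDF. The SHAPS and HAM-A rows have no mark in any follow-up cell, so the reading is unaffected.

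**3. Distance from screening to infusion.** Research Design and Methods gives a minimum commitment of 4 weeks, at least 7 days between infusions, and an upper limit: "The total commitment should not exceed 3 months". The schedule ends with a call 7 days after infusion 2. Taking 3 months as about 13 weeks and the other intervals at their minimum:

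- 4-week commitment: 4 − 1 − 1 = 2 weeks to infusion 1, and 4 − 1 = 3 weeks to infusion 2.
- 3-month limit: 13 − 1 − 1 = 11 weeks to infusion 1, and 13 − 1 = 12 weeks to infusion 2.

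Each is the longest gap for that total commitment. Patients enter on symptom severity (EPDS above 12 or HAM-D above 14), and the Justification section rules out a placebo group. Natural course and regression to the mean over this gap therefore cannot be separated from drug effect.

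**4. State of the patient at the post-dose rating.** Patients rest for 2 to 4 hours after the infusion and may then complete questionnaires. With the stated half-life of 2–3 hours, the fraction of the end-of-infusion level remaining is 2^(−t/half-life):

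- t = 2 h: 2^(−2/2) = 0.50 to 2^(−2/3) = 0.63
- t = 4 h: 2^(−4/2) = 0.25 to 2^(−4/3) = 0.40

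The section on risks describes "The most commonly reported side effects during the 4 hour period after each infusion" and includes feeling strange, abnormal sensations and sleepiness. Hypothesis 3 expects fewer side effects at 0.2 than at 0.5 mg/kg. On the protocol's own expectation, the disturbance differs by dose, so randomized order does not remove it from the dose contrast.

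**5. Carry-over.** Let A and B be the effects of the two doses, and let a fraction r of the infusion-1 effect persist at infusion 2. Sequence AB yields A, then B + rA; sequence BA yields B, then A + rB. The within-patient differences are (A − B) − rA and (A − B) + rB. Averaged over balanced sequences, they give (A − B)(1 − r/2).

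Assuming r = 0.20 to 0.35, the dose difference shrinks by 10% to 17.5%. The documents do not give r. Their one-week figure of up to 35% counts patients still responding and is not a fraction of a SHAPS effect. A residue equal for both doses would cancel. Without a SHAPS score before infusion 2, none of this can be examined.

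**6. What can still be estimated.** Two contrasts remain: screening to after infusion 1, and the within-patient difference between the two after-infusion scores. With n = 10 and a two-sided 0.05 test, the second has 80% power for a standardized paired difference of about 1.00 and 90% for about 1.15. Not available are change from a same-day baseline for either infusion, a period-2 baseline, and any 24-hour effect.

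**The case against.** A reader might infer from the blank cells that the SHAPS question cannot be answered for either dose. The documents do not support that. Screening is an untreated reference for infusion 1. Order is randomized and balanced, so the two after-infusion scores give a dose comparison that needs no baseline. The algebra above shows carry-over attenuating that comparison, not abolishing it.

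It is also tempting to express the loss as a multiple of the sample size. That would need correlations between SHAPS ratings, which the documents do not give, and screening cancels from the within-patient dose difference in any case.

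Three further objections have force:

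- The protocol ties SHAPS to no time point. The 24-hour standard belongs to HAM-D-17 and to Hypothesis 2, and the Background expects mood to improve within about 2 hours. An early SHAPS score is therefore legitimate as an early reading. This stands, but the score remains exposed to dose-dependent acute effects and cannot be compared with the primary result.
- The 11 to 12 weeks is an extreme; the minimum commitment gives 2 to 3. This stands, and the range should be quoted whole.
- The text has all questionnaires completed on the infusion day and has the calls collect unnamed mood questionnaires. This could be read as covering SHAPS, but neither statement places a SHAPS score before dosing or at 24 hours, and the table leaves those cells blank.

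The measure is also exploratory and supports no numbered hypothesis. That lowers the severity.

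**Conclusion.** The point holds as a minor design weakness. SHAPS has three scheduled readings per patient, none before an infusion and none at 24 hours. Its exploratory purpose can be pursued only through a change from screening over a variable gap (up to 2–3 weeks at the minimum commitment, up to 11–12 weeks at the limit, with no placebo arm) and a dose contrast taken hours after dosing.

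The gap figures follow from the stated limits, with the other intervals at their minimum. The 25–63% residual drug level follows from the stated half-life; it shows that drug is still present, not that a SHAPS score is invalid. The 10–17.5% attenuation rests on an assumed r.

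The same schedule pattern matters more for HAM-A, because Hypothesis 2 names HAM-A at 24 hours and the schedule provides no such reading.

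**What to change.** - **Schedule.** Mark SHAPS at Before Infusion on both infusion days and at the Day 1 call after each infusion. Optionally add the Day 7 call after infusion 2. Do the same for HAM-A, so that Hypothesis 2 can be tested at the time it names.
- **Text.** Align the sentence on infusion-day questionnaires with the table by saying which scales are completed before and which after dosing.
- **Analysis plan.** Add one sentence: an exploratory within-patient comparison of 24-hour SHAPS between doses, using each infusion's own pre-infusion score. Keep the existing after-infusion score as an early reading. Report the pre-infusion-2 score against the pre-infusion-1 score, so that any residue is visible, although natural course will still be mixed in.

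For SHAPS this adds four administrations per patient, or five with Day 7, at contacts that already collect similar scales. The downside is a few minutes of patient time at each, and somewhat more once HAM-A is included.
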